1. PROTOCOL SYNOPSIS

Name of Sponsor/Company: Soligenix, Inc.	
Name of Investigational Product: SGX942 (dusquetide), sterile solution for intraven	nous (IV) infusion
Name of Active Ingredient: Dusquetide (research name SGX94). fully s	synthetic novel pentapeptide
Title of Study: A Pivotal, Double-Blind, Randomized, Placebo-Controll (Dusquetide) for the Treatment of Oral Mucositis in Pat Chemoradiation for the Treatment of Squamous Cell Carcinon	ients Being Treated with Concomitant
Study Center(s): A total of 50-60 centers in the USA and EU	
Principal Investigator:	
Studied Period (years): Estimated date first patient enrolled: November 2017 Estimated date last patient enrolled: March 2020	Phase of Development: Phase 3

Objectives:

Primary Objective:

 To assess the efficacy of SGX942 compared to placebo in decreasing the duration of severe oral mucositis (SOM; defined as World Health Organization [WHO] Grade lesion ≥3) in patients receiving fractionated radiation treatments and concomitant cisplatin chemotherapy, given as 80-100 mg/m² every third week, for the treatment of squamous cell carcinoma of the oral cavity or oropharynx.

Secondary Objectives:

To assess the impact of SGX942 compared to placebo on the following clinically important secondary objectives:

- To assess the impact that SGX942 has on the Area-Under-the-Curve (AUC) for SOM (WHO Grade ≥3) by time plot (severity-weighted duration)
- 2. To assess the impact that SGX942 has on the Area-Under-the-Curve (AUC) for ulcerative oral mucositis (UOM; defined as WHO Grade ≥2) by time plot (severity-weighted duration)
- 3. To assess the impact that SGX942 has on the incidence of SOM
- 4. To assess the impact that SGX942 has on the quality of life assessment using the European Organization for Research and Treatment of Cancer (EORTC) Quality of Life Question for Head and Neck Cancer 43 question (QLQH& N43) instrument
- 5. To assess the impact that SGX942 has on the amount of opioids used

To assess the impact of SGX942 compared to placebo on the following additional secondary objectives:

- To assess the impact that SGX942 has on the cumulative number of days of RT breaks
- To assess the impact that SGX942 has on the duration of SOM; in all randomized patients receiving fractionated RT and concomitant cisplatin chemotherapy, given as 80-100 mg/m²

Original: 11 January 2017 Confidential Page 3 of 67

every third week (ITT population)

- To assess the impact that SGX942 has on the duration of UOM
- To assess the impact that SGX942 has on the cumulative amount of pain reported by patients
- The duration of SOM using an alternative definition calculated as the number of days from the first oral examination with WHO grade ≥3 through the last assessment with a WHO score ≥3 (and not to the first assessment with a WHO grade <3) with no further reports of a WHO grade >3.
- The duration of SOM in the Per-Protocol Population defined as patients receiving a cumulative radiation dose of at least 55 Gy and having received all study drug scheduled.

Safety Objective:

Safety objectives will include the following:

- To assess the impact that SGX942 has on the Adverse Events (AE) and serious Adverse Events (SAE)
- To assess the impact that SGX942 has on changes in safety laboratory values
- To assess the impact that SGX942 has on the Response Evaluation Criteria in Solid Tumors (RECIST) categorization of the primary tumor at 12 weeks and 12 months post-CRT
- To assess the impact of SGX942 on the incidence of reported presumed bacterial infections between Baseline and 6 weeks after completion of radiation therapy (RT) by total number and by severity of infection, graded using the National Cancer Institute's (NCI's) Common Terminology Criteria for Adverse Events (CTCAE)
- To assess the impact of SGX942 on 12 month all-cause mortality
- To assess the impact of SGX942 on progression free survival through 12 months

Methodology:

Approximately 260 patients with squamous cell carcinoma of the oral cavity and oropharynx scheduled to receive a minimum total cumulative radiation dose of 55 Gy fractionated as 2.0-2.2 Gy per day and concomitant cisplatin chemotherapy given as a dose of 80-100 mg/m² (every third week) will be enrolled. Subjects will be randomized to receive either 1.5 mg/kg SGX942 or placebo given as a 4-minute IV infusion using an infusion or syringe pump. Blinded study drug will be started within 3 days after starting RT and continued twice a week (2-4 calendar days apart) through 2 weeks after completion of the RT. Efficacy will be assessed by oral examination at each treatment visit and then at the 3 through 6 weeks post-RT completion visits. OM will be evaluated using the WHO Grade system and performed by observers trained on these measurements. SOM is defined as a WHO Grade of \geq 3. The duration of SOM is defined as the first time the patient has a WHO Grade \geq 3 until the first time the patient has a WHO Grade of <3 with no subsequent readings \geq 3. Patients will be randomized (1:1; 1.5 mg/kg SGX942:placebo) using an interactive web response system (IWRS). Randomization will be stratified by site, presence of prophylactic gastrostomy feeding tube, and tumor human papillomavirus (HPV) status.

Routine clinical chemistry and hematology will be obtained at Screening/Baseline, then at 3, 6, and 9 weeks while receiving study drug, and then at the 4 and 6 week post-RT completion visit. The same type of scan initially used to stage the tumor (i.e., computed tomography [CT], magnetic resonance imaging [MRI] or positron emission tomography [PET]) will be repeated at 12 weeks and 12 months after completion of the radiation therapy and compared to the initial scan using the RECIST 1.1 criteria.

Number of Patients (planned):

260 patients (130 SGX942 treated and 130 placebo treated patients) will be enrolled.

Diagnosis and Main Criteria for Inclusion:

Inclusion Criteria

Patients must meet *all* of the following criteria in order to be eligible for enrollment:

- 1. Willing and able to understand and sign an informed consent
- 2. Males or females age greater than or equal to 18 years
- 3. Biopsy-proven squamous cell carcinoma of the oral cavity or oropharynx without distant organ metastases that has been evaluated for human papillomavirus (HPV)
- Scheduled to receive cisplatin chemotherapy of 80-100 mg/m² given every third week
- 5. Scheduled to receive a continuous course of conventional external beam irradiation delivered by intensity-modulated radiotherapy (IMRT) as single daily fractions of 2.0 to 2.2 Gy, with a cumulative radiation dose between 55 and 72 Gy at each site
- 6. Planned radiation treatment fields must include at least 2 oral sites (retromolar trigone, buccal mucosa, floor of mouth, tongue, or soft palate), with each site receiving ≥55 Gy
- 7. All women of childbearing potential (WOCBP) and males with female partners who are WOCBP must agree to the use of effective contraception during the trial.
 - Women are considered to be WOCBP following menarche and until becoming postmenopausal unless permanently sterile (hysterectomy, bilateral salpingectomy and bilateral oophorectomy). A postmenopausal state is defined as no menses for 12 months without an alternative medical cause.
 - Effective contraception methods for WOCBP should be started prior to randomization and continued for a minimum of 35 days following completion of study drug administration.
 - Acceptable contraceptive methods for WOCBP are those that achieve a failure rate of less than 1% per year and include:
 - Combined (estrogen and progestogen containing) hormonal contraception associated with inhibition of ovulation:
 - Oral
 - Intravaginal
 - Transdermal
 - Progestogen-only hormonal contraception associated with inhibition of ovulation:
 - Oral
 - Injectable
 - Implantable
 - o Intrauterine device (IUD)
 - o Intrauterine hormone-releasing system (IUS)
 - Bilateral tubal occlusion
 - Vasectomized partner
 - Sexual abstinence defined as refraining from heterosexual intercourse during the entire period of risk associated with the study treatments
- Male subjects should use condoms during treatment and for 98 days following the last study drug administration period.

Exclusion Criteria

Patients with any of the following criteria are **NOT** eligible for enrollment:

1. Current mucositis

Amendment 3: 17 September 2019

- Current, clinically significant, active infection that in the opinion of the Investigator would make them an unfit participant in the trial
- Planned to receive Erbitux[™] (Cetuximab) or similar targeted therapy between Baseline and 6 weeks post-RT
- 4. Current use of prohibited therapies listed in Section 8.2
- 5. Prior radiation to the head and neck
- 6. Chemotherapy treatment within the previous 12 months
- Tumors of the lips, sinuses, salivary glands, nasopharynx, hypopharynx, or larynx
- Evidence of significant renal, hepatic, hematologic, or immunologic disease determined by any
 one of the following: (the below are examples of evidence of significant disease, not required
 tests)
 - A. Estimated creatinine clearance <30 mL/min

 - B. ALT or AST level greater than 10-fold the upper limit of normal or total bilirubin greater than 3-fold the upper limit of normal
 - C. Manifestations of end-stage liver disease, such as ascites or hepatic encephalopathy
 - D. Thrombocytopenia (less than 60,000 cells/mm³)
 - E. CD4+ T cell count below 200 cells per μL (verification only required if there is a clinical diagnosis of HIV infection)
- 9. Evidence of immediate life-threatening disease or a life expectancy of less than 3 months
- 10. Women who are pregnant or breast-feeding
- 11. Participation in any study involving administration of an investigational agent within 30 days of randomization into this study
- 12. Any condition that, in the opinion of the Investigator, would compromise the safety of the subject or quality of the data

Investigational Product, Dosage, and Mode of Administration:

Dusquetide is a pentapeptide that is a first in class Innate Defense Regulator (IDR). SGX942 is dusquetide formulated for IV infusion.

The diluted solution will be administered as a 4-minute IV infusion using an infusion or syringe pump. Patients will be treated twice a week (2-4 calendar days apart) starting within 3 days after initiating RT and continuing through 2 weeks after completion of the RT. Patients missing more than 5 sequential scheduled RT sessions will be withdrawn from the trial.

Duration of Treatment:

Patients will start study drug infusions within 3 days after starting RT and continue through 2 weeks after completion of RT. RT is typically scheduled to continue for 5 to 7 weeks, if there are no breaks in treatment. Since distinct treatment breaks of up to 1 week may be encountered, the expected study drug treatment duration will be from 6 to 11 weeks.

Reference Therapy, Dosage, and Mode of Administration:

Placebo will consist of 0.9% sodium chloride (normal saline) that is identical in appearance to active drug. Blinded vials of placebo will be diluted identically to that of active drug to a final volume of 25 mL and infused using an infusion or syringe pump over 4 minutes. The frequency and duration of therapy will be identical to the active drug.

Original: 11 January 2017 Confidential Page 6 of 67

Criteria for Evaluation:

Efficacy:

Efficacy will be determined in patients who have received enough radiation exposure to put them at significant risk of developing SOM (defined as a cumulative radiation dose of at least 55 Gy).

Primary Endpoint:

The primary efficacy outcome for this study is the duration of SOM, defined as the number of days from the first oral examination with a WHO Grade assessment of ≥ 3 until the first time the patient has a WHO Grade of ≤ 3 with no subsequent readings ≥ 3 .

Secondary endpoints will be analyzed in hierarchical order:

- The Area-Under-the-Curve (AUC) for SOM (WHO Grade ≥3) by time plot (severity-weighted duration)
- The Area-Under-the-Curve (AUC) for ulcerative oral mucositis (UOM; defined as WHO Grade ≥2) by time plot (severity-weighted duration)
- The incidence of SOM
- 4. The quality of life assessment using the European Organization for Research and Treatment of Cancer (EORTC) Quality of Life Questionnaire 30 question module (EORTC QLQ-C30 (version 3)) and the EORTC Head and Neck Cancer latest 43 question module (QLQ-H&N43) instrument
- 5. The amount of opioids used

The following secondary endpoints will also be examined:

- The cumulative number of days of radiation treatment breaks
- The duration of SOM in all randomized patients receiving fractionated RT and concomitant cisplatin chemotherapy, given as 80-100 mg/m² every third week (ITT population)
- The duration of UOM
- The cumulative amount of pain reported by patients
- The duration of SOM using an alternative definition calculated as the number of days from the first oral examination with WHO grade ≥3 through the last assessment with a WHO score ≥3 (and not to the first assessment with a WHO grade <3) with no further reports of a WHO grade >3.
- The duration of SOM in the Per-Protocol Population defined as patients receiving a cumulative radiation dose of at least 55 Gy and all scheduled study drug.

Safety:

- The incidence, type, and body system categorization of AEs
- The incidence, type, and body system categorization of SAEs
- The changes from Baseline for hematology parameters, clinical chemistry parameters, and vital signs
- Tumor status at 12 weeks and 12 months following completion of RT categorized using the RECIST criteria

Confidential

- The incidence and severity of reported infections assessed by CTCAE grading
- The 12 month post-RT survival

Statistical Methods:

The primary analysis will be a log-rank test of the differences in the duration of SOM between the 1.5 mg/kg SGX942 and placebo treated groups. A log-rank test will be used to compare the AUC of the WHO Grade-time curve and the number of days to onset of OM. The incidence of SOM and UOM, percent of RECIST complete responders, percent of patients with presumed bacterial infections and severity of infections will be compared using chi-squared tests. The primary analysis population will be all patients receiving drug who have received enough radiation exposure to put them at significant risk of developing SOM (defined as a cumulative radiation dose of at least 55 Gy).

Original: 11 January 2017 Confidential

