It is assumed that patients will receive 7 weeks of RT. In practice, some patients will have a shorter course (lower planned radiation dose) or stop treatment early. Similarly, patients with RT breaks who complete 7 weeks of RT may require treatment for more than 7 weeks. All post-RT visits will be scheduled from the last RT so that if the RT is completed after 6 weeks, study drug will be continued for the 2 weeks following (Weeks 7 and 8) and the 12 weeks post-radiation scan will be obtained in Week 18. Similarly, if there are treatment breaks such that RT completes in study Week 8, the study drug will continue for 2 weeks (Weeks 9 and 10) and the 12 weeks post-radiation scan will be obtained at Week 20.

6.2. **Specific Assessments**

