6.3.3 Study Drug Administration Visits During RT

Study visit days occur twice weekly (every 3 days +/-1 day) through the completion of RT. The first study visit must occur within 3 days of initiating RT. The study visit schedule should be adhered to and is independent of CRT administration. At study drug administration visits, the following will be performed:

- Interim Medical History
- Vital signs
- Adverse events
- Clinical evaluation of mucositis (WHO Score)
- Record details of percutaneous endoscopic gastrostomy (PEG) tube use (if applicable)
- Study Drug administration
- History of pain and opioid use
- Assessment of Infections
- Quality of Life assessment (Week 4 only)
- In addition to the above, routine safety laboratories will be obtained during Weeks 3 and 6 for:
 - Blood collection for hematology and clinical chemistry panel

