7.3. Patient Withdrawal Criteria

Patients have the right to withdraw from this trial at any time (as described in the informed consent document) without prejudice to further care. An investigator may withdraw a patient from the study at any time for any of the following reasons:

- The patient withdraws his/her consent or refuses follow-up evaluations.
- The patient is lost to follow-up and will not attend further study visits.
- The investigator determines that further participation would be detrimental to the patient's health or well-being.
- The patient fails to comply with the study requirements to cause harm to self or seriously interfere with the validity of the study results.
- The female patient becomes pregnant during the treatment period. In this case, treatment should be halted and the patient followed until the end of the pregnancy. If a child is born, the infant should be followed through at least 6 months of age.
- At the discretion of the site investigator if he/she feels that it is in the best medical interest of the patient.
- The patient misses more than 5 consecutive scheduled RT sessions.
- Patients withdrawn from the study will have as many of the trial assessments completed
 as the patient permits including blood tests and scans but not including OM scoring. All
 other therapies including radiation therapy, the type and frequency of chemotherapy, and
 oral treatments will remain at the discretion of the clinical team. Patients will be censored
 in the efficacy analyses at the time of withdrawal.
- Patients withdrawn from the trial will not be replaced but enrollment will continue until a minimum of 260 patients have been enrolled.

7.4. **Termination of the Study**

The study may be terminated early for any of the following reasons:

- A health authority or DMC requests termination of the study.
- It has been determined that the risk level associated with the experimental drug is significant and warrants termination of the study.
- Soligenix, for reasons other than safety, may terminate the study at any time by written notice of intended termination provided at least thirty (30) days prior to termination.
- The investigator or IRB/EC, for reasons other than safety, may terminate participation of this site in the study by written notice of intended termination provided at least thirty (30) days prior to termination.

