12.5. Selection of Primary Analysis Population

Given that OM does not occur at a significant rate in patients that have not received at least 55 Gy of cumulative radiation, the primary analysis population will be limited to those patients that have received at least 55 Gy of radiation. Only those patients that receive sufficient radiation therapy are at risk of developing the disease (i.e., SOM). Should SGX942 reduce the most severe cases of OM prior to reaching 55 Gy of radiation such that there is a reduced dropout rate from anticancer therapy, the worst cases of OM in the placebo group, but not the SGX942 group, will be eliminated from the analyses. Thus, if bias is introduced, it is likely to lead to a conclusion that SGX942 is less efficacious than it actually is.

The primary efficacy analysis will be based on this mITT population that is defined as all randomized subjects receiving a minimum of 55 Gy of cumulative radiation analyzed per treatment groups defined by their randomization treatment assignment.

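### A long RT break can lead to trial withdrawal, which stops mucositis scoring: SOM duration is then censored and both AUCs are cut short for a reason plausibly linked to severity

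*Protocol*

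**What the plan says.** The Synopsis (Investigational Product, Dosage, and Mode of Administration) makes withdrawal mandatory: "Patients missing more than 5 sequential scheduled RT sessions will be withdrawn from the trial". Protocol 7.3 makes it discretionary. Its list opens with "An investigator may withdraw a patient from the study at any time for any of the following reasons", and one entry is "The patient misses more than 5 consecutive scheduled RT sessions".

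The consequence is the same under either text:
- Protocol 7.3 continues the other assessments "as the patient permits including blood tests and scans but not including OM scoring", and censors the patient "in the efficacy analyses at the time of withdrawal".
- Protocol 10.1 and SAP 9.1 censor an unresolved SOM episode at the 6-week post-RT visit, or at discontinuation if that comes sooner.
- Protocol 10.2.1.1 and 10.2.1.2 and SAP 9.4.1 compute the SOM and UOM AUC only as far as the last WHO score on record.
- SAP Appendix 1, section 4 carries scores forward no further than discontinuation. It adds two sensitivity analyses (last grade held for the whole trial, and grade 0) under a heading about SOM duration. Neither document gives such a rule for the AUCs.

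The visit calendar does not depend on RT being given. Protocol 6.3.3 says of visits during RT: "The study visit schedule should be adhered to and is independent of CRT administration". For later visits, Protocol 6.1 says: "All post-RT visits will be scheduled from the last RT". Protocol 7.3 leaves RT after withdrawal to the clinical team. SAP 3.2.3 requires 55 Gy for mITT without saying whether RT given after withdrawal counts.

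**The concern.** The score that defines the primary endpoint is the one assessment that Protocol 7.3 drops at withdrawal, although blood tests and scans are still requested. The mixed wording also lets sites apply the rule differently.

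The loss is plausibly related to outcome. Protocol 12.5 considers that if the drug reduces severe OM before 55 Gy, "there is a reduced dropout rate from anticancer therapy". The cumulative duration of RT breaks is itself a secondary endpoint (SAP 9.4.6), so the sponsor treats breaks as something the drug may change. If patients with long SOM are more likely to have a long break, the log-rank test loses long episodes to informative censoring.

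The AUCs are more exposed. They have no censoring mechanism, so a curve cut short simply counts as less disease. They are also the first two steps of the fixed sequence (SAP 9.3.1), and a failure at either one closes formal testing of everything below it.

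**Working it through.** **1. The plan's own sample size.** Protocol 12.4 assumes medians of 13 and 8 days, 90% power and alpha 0.05 (two-sided per SAP 3.3), and states 95 evaluable patients per arm. With HR = 8/13 = 0.615, Freedman's formula gives (1.960 + 1.282)² × ((1 + 0.615)/(1 − 0.615))² = 10.51 × 17.64 = 185.4, so 186 events. That reproduces 190 within 3%. Schoenfeld gives 4 × 10.51/(ln 0.615)² = 179. The 190 therefore treats nearly every evaluable patient as an observed resolution.

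**2. Primary test.** No break rate is given, so 2%, 5% and 10% of placebo mITT patients are assumed. The simulation (20,000 trials per setting, Monte Carlo error about 0.2 points) assumes:
- exponential durations with visits every 3.5 days, and SOM in every patient;
- break risk proportional to SOM duration, so 10% in placebo means about 10% × 8/13 = 6.2% in SGX942;
- break start uniform over the first 28 days of the episode, with withdrawal 8 days later, censoring only if SOM is unresolved;
- in the comparison without withdrawal, a break leaves SOM duration unchanged.

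Power without withdrawal → with withdrawal:

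| Placebo break rate | Episodes censored, of 190 | Log-rank, 95/arm | Log-rank, 110/arm (assumed) | SOM AUC (ANOVA), 95/arm | SOM AUC (ANOVA), 110/arm |
|---|---|---|---|---|---|
| 2% | 1.9 | 90.7 → 90.3 | 94.6 → 94.3 | 90.5 → 89.6 | 94.6 → 93.8 |
| 5% | 4.9 | 90.7 → 89.1 | 94.5 → 93.5 | 90.5 → 87.6 | 94.6 → 92.3 |
| 10% | 9.7 | 91.1 → 88.4 | 94.2 → 92.1 | 91.0 → 84.9 | 94.2 → 89.1 |

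If a 10% break rate applied equally to both arms and was unrelated to duration, power would go from 91.1% to 90.3% with the hazard ratio unchanged. It is the link with duration that matters.

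**3. Direction (10%, 95 per arm).** Breaks in placebo only move the resolution hazard ratio from 1.544 to 1.501 (log-rank power 86.3%). Breaks in SGX942 only move it to 1.585 (power 93.1%).

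**4. Type I error.** With equal medians, and break risk depending on duration in the same way in both arms, log-rank rejection is 5.0–5.5% without withdrawal and 4.8–5.4% with it.

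**5. If the break speeds healing.** Scoring was continued through the break and the remaining SOM shortened, at 10% and 95 per arm (separate runs, one of them with 4,000 trials per setting). With the remainder halved, power under continued scoring is 88.8–89.9%. With the remainder cut to a quarter it is 86.4–87.1%. The current rule gives 88.4–88.6% in the same runs. At 110 per arm the figures are 92.5% and 90.0%, against 91.4% under the current rule.

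**6. AUC.** At 10% and 95 per arm, mean SOM AUC falls from 56.6 to 50.4 in placebo and from 34.9 to 33.4 in SGX942. The difference shrinks from 21.7 to 17.0, a loss of 4.7/21.7 = 22%. With breaks in placebo only, SOM AUC power falls from 90.4% to 71.3% (4,000 trials). For one invented patient at grade 3 from day 28 to day 59.5, the trapezoid gives 105. If scoring stops at day 42 it gives 47.25, or 45% of that.

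**7. Who reaches mITT.** If RT after withdrawal does not count, the break must start after 55 Gy. At 2.0 Gy that takes 28 fractions and the 72 Gy maximum is 36, leaving 8/36 = 22%. At 2.2 Gy it is 25 of 32, leaving 7/32 = 22%. At lower doses the share is smaller: 7/35 = 20% at 70 Gy and 2/30 = 7% at 60 Gy, both in 2.0 Gy fractions. If breaks are spread evenly over the fractions, a 10% overall rate then puts about 10% × 22% = 2.2% into mITT, close to the 2% row.

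**The case against.** The strongest reply is that the table overstates what continued scoring would gain, because its comparator leaves SOM untouched by a break of more than a week. Step 5 bears this out: the power difference can shrink or reverse. Censoring at a long break is also a defensible choice when entry requires a continuous RT course. This stands, and it is why no gain in primary power is claimed.

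The inputs also lean high. The Synopsis expects breaks of up to one week, which is five sessions and does not trigger the rule. Not every patient will have SOM, and the simulation does not check that RT is still running when the break starts. A patient who misses RT may not attend for an examination either, since Protocol 8.3 places infusions at the RT appointments. These points make the effects smaller, but they do not explain why a willing, attending patient should go unscored.

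SAP Appendix 1, section 4 already bounds the primary endpoint. That stands for SOM duration, but its heading does not reach the AUCs. The AUC losses were computed only for the SAP's ANOVA, whereas Protocol 12.1 names a log-rank test for AUC. The size under that test has not been worked out.

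A reader might infer that the rule biases the trial in favour of SGX942. The documents do not support this. Protocol 12.5 is conditional, concerns dropout before 55 Gy, and expects any bias to run against the drug. The placebo-only case above agrees. A shift in the drug's favour needs more long breaks on SGX942, the opposite of what fewer long SOM episodes would produce.

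**Conclusion.** The point holds as a modest, avoidable weakness. The two passages disagree on whether withdrawal is required, and both lead to censoring and AUC truncation plausibly linked to SOM severity.

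For the primary test, the difference is 0.3 to 2.7 points at assumed break rates of 2–10% if breaks do not shorten SOM, and it may be nil or reversed if they do. At an assumed 110 mITT patients per arm (of 130 enrolled), power under the current rule stays above 90% (91.4–92.1% at the 10% rate). Type I error is not inflated when the drug has no effect and breaks follow SOM alike in both arms. The null runs did not cover a drug effect on breaks by another route.

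The SOM AUC is more exposed: 0.9 to 6.1 points at 95 per arm under ANOVA, and about 19 points (90.4 − 71.3) in the extreme case of 10% breaks in placebo only. If RT after withdrawal does not count towards 55 Gy, at most about 22% of breaks reach mITT, the effect there is near zero, and the issue sits mainly in the ITT analysis. A reader should not conclude that the primary result is in jeopardy; no figure here shows that.

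**What to change.** - Align the Synopsis and Protocol 7.3: missing more than 5 consecutive RT sessions may stop study drug but is not a reason for trial withdrawal.
- In 7.3, remove the exclusion of OM scoring, so that any withdrawn patient who agrees is scored at the scheduled visits through 6 weeks post-RT.
- In SAP 9.1 and 9.4.1, state that observed scores are used and that censoring occurs only when scoring ends. Add censoring at the RT break as a sensitivity analysis.
- For patients already withdrawn, extend the two bounding analyses of SAP Appendix 1, section 4 to the SOM and UOM AUC.

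The cost is a minor amendment, a few SAP sentences and a few more oral examinations at visits already on the calendar. The trade-off is that observed durations will include any healing during the break, which the added sensitivity analysis would show. Scores already lost cannot be recovered.
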